**Principal Investigator:**  
**IRB Tracking Number:** 20170730  
**Submission Notes:** There was a typo on page 5 of the WIRB document. In the section that describes the secondary rescue maneuver we mention sat> 94% which should be 90% instead as illustrated in attachments A (page 9) and B (pages 10).  
 This did not affect the results of our trial as none of our patients needed to have a secondary rescue maneuver.  
**Sponsor Name:** Bristol Hospital

**Submitted Files:**

File	Type
corrected wirb research proposal bh use of non invasive positive pressure ventilation in obese pts undergoing upper gi endoscopy procedures final 3 23 17.docx.pdf	Protocol/Grant
corrected wirb research proposal bh use of non invasive positive pressure ventilation in obese pts undergoing upper gi endoscopy procedures final 3 23 17.docx.pdf	Miscellaneous

## **Use of Non-invasive Positive Pressure Ventilation for Obese Patients Undergoing Upper GI Endoscopy Procedures**

### **ii. Purpose of the study:**

The aim of our study is to evaluate the effect of non-invasive positive pressure ventilation (BiPAP) in severely obese patients undergoing upper endoscopy both as an adjunct to sedation to decrease the incidence of hypoxic episodes, and as a rescue maneuver in case a hypoxic episode occurs.

Hypothesis: Use of non-invasive positive pressure ventilation in morbidly obese patients (BMI >40) will improve oxygen saturation during upper GI endoscopy procedures.

**Background:** Current estimates of the prevalence of severe obesity are 5.5 % in males and 9.9% in females. Obesity constitutes a major health problem and bariatric surgery is currently the most effective and sustainable treatment option especially for patient with severe obesity (BMI >40). (Flegal, 2016)

Many patients being evaluated for bariatric surgery undergo screening upper endoscopy, although this practice has been challenged recently. Our center has adopted a universal screening policy in the evaluation of patients undergoing bariatric surgery.

Sedation is widely performed during endoscopy to decrease patient anxiety, discomfort and pain. Obesity has been identified as an independent risk factor for sedation-related adverse events, such as hypoxia and need for airway maneuvers, in patients undergoing endoscopy. Non-invasive positive pressure ventilation is commonly used in hospitals to supplement oxygenation and ventilation, especially in the morbidly obese patients. Our hypothesis is that use of non-invasive positive pressure ventilation in morbidly obese patients (BMI>40) will improve oxygen saturation during upper GI endoscopy procedures.

### **iii. Criteria for Subject Selection**

**Title:** Use of Non-invasive Positive Pressure Ventilation for Obese Patients Undergoing Upper GI Endoscopy Procedures

**Number of participants:** 88

**Gender of Subjects:** Male; female

**Age of Subjects:** 18-65 years of age

**Racial and Ethnic Origin:** No race or ethnic origin restrictions

**Inclusion Criteria:**

The following patients will be included in this research study:

- Patients undergoing screening upper endoscopy prior to weight loss surgery
- BMI 40-60

**Exclusion Criteria:**

The following patients will be excluded from this research study:

- Pregnant patients
- Previous weight loss surgery or stomach surgery

- BMI > 60 and BMI < 40
- Active smokers
- Patients with a history of recent URTI (Upper Respiratory Tract Infection) within the preceding 2 weeks
- Lung disease, COPD asthma, cystic fibrosis, sarcoidosis
- Baseline O2 saturation less than or equal to 94%
- Exclude substance abusers (active alcohol abuse, benzodiazepine abuse, active illicit drug use)

#### **iv. Methods and Procedures.**

This study is an Effectiveness trial.

#### **End points to be measured with definitions**

Monitoring vital signs every 2-3 minutes unless there is an event:

1. O2 saturation
  - Desaturation defined as O2 sat  $\leq$  94%
  - Desaturation requiring intervention O2 sat < 90 %
2. Heart rate
3. Blood pressure
4. Respiratory rate:
  - In the control group this will be obtained from the ETCO2 monitor
  - In the treatment group this will be measured by the BiPAP machine
5. Procedure times
  - Time of start of sedation (time 0/start time)
  - Time of scope in patient
  - Time of scope out of patient
  - Time to patient opens eyes to verbal stimuli (end time) as end of procedure
6. Number of endoscope withdrawing events during procedure
7. Number of procedure cancellations after induction with propofol
8. Measure age, sex, neck circumferences, ASA score, Mallampati score, BMI and end points
9. Total dose of propofol per patient

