**Data Analysis and Data Monitoring.**

Statistical power was calculated to detect a significant treatment effect for the desaturation primary outcome based on a chi-square goodness of fit test for the difference between the treatment and control group in the likelihood of a desaturation event. Assuming a moderate effect size for the difference between the two groups in the probability of a desaturation event (Cohen's  $w=.30$ ), a total of  $N=88$  participants ( $N=44$  per study arm) are required to achieve acceptable statistical power of 0.80 for a two-tailed test with  $\alpha=0.05$ .

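### The desaturation cut lies one point below the lowest eligible baseline saturation, yet that baseline is neither listed for recording nor used in the analysis

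*Combined protocol and SAP*

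**What the plan says.** - **Event.** *End points to be measured with definitions*, item 1, has two tiers: "Desaturation defined as O2 sat" of 94% or less, and "Desaturation requiring intervention O2 sat < 90"%. Neither has a duration, a confirming reading, an artefact rule or a change from baseline.
- **Schedule.** The same section sets "Monitoring vital signs every 2-3 minutes unless there is an event".
- **Entry.** *Exclusion Criteria* rules out "Baseline O2 saturation less than or equal to 94"%. In whole-number readings the lowest eligible value is 95%.
- **Characteristics recorded.** Item 8 reads "Measure age, sex, neck circumferences, ASA score, Mallampati score, BMI and end points". Baseline saturation is not among them.
- **Analysis.** *Data Analysis and Data Monitoring* powers the trial for a "significant treatment effect for the desaturation primary outcome". It uses a chi-square test of the difference between arms "in the likelihood of a desaturation event". No tier is named and no covariate is used.
- **Aim.** *Purpose of the study* gives the aim of BiPAP as an adjunct: "to decrease the incidence of hypoxic episodes".

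**The concern.** The outcome is a yes/no event at a fixed cut, and the eligibility limit sits directly against that cut. How far a patient must fall to be counted is set largely by the value at entry: one point from 95%, three from 97%, six from 100%. A variable that separates patients this way is the obvious one to carry into the analysis, and the trial already has it.

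Leaving it out has two consequences. Variation due to entry saturation stays in the comparison as noise, and a chance difference in entry saturation between two groups of 44 passes straight into the event rates. Separately, with no confirmation rule, a patient resting near 95% can be scored as an event on measurement error alone. That blurs an outcome meant to represent hypoxic episodes.

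**Working it through.** **1. The plan's own figure.** Inputs from *Data Analysis and Data Monitoring*: w = 0.30, two-sided alpha 0.05, power 0.80.

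N = (1.960 + 0.842)² / 0.30² = 87.2, rounded up to 88. Noncentral chi-square power at N = 88 is 0.80. The sample size reproduces. The plan gives no event rates. Two pairs that correspond to w = 0.30 are used below:
- 65% v 35%: 0.30 / (2√(0.5 × 0.5)) = 0.30
- 43.75% v 16.25%: 0.275 / (2√(0.3 × 0.7)) = 0.30

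**2. How much the starting level matters near the cut.** Assumptions not in the documents: steady true saturation S, whole-number display, independent normal reading error, 5 readings.

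Per-reading chance p = Φ((94.5 − S)/SD). Chance of at least one reading of 94% or less = 1 − (1 − p)⁵. For S = 95 and SD 1: p = Φ(−0.5) = 0.309, and 1 − 0.691⁵ = 0.84.

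| Steady level | SD 0.5 | SD 1 | SD 1.5 |
|---|---|---|---|
| 95% | 0.58 | 0.84 | 0.90 |
| 96% | 0.01 | 0.29 | 0.58 |
| 97% | 0.00 | 0.03 | 0.22 |
| 98% | 0.00 | 0.00 | 0.05 |

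Error that is correlated within a patient would make these smaller. The gradient is steep between 95% and 97% and nearly gone by 98%.

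**3. Chance imbalance in baseline.** Assume random allocation, baseline SD 1.4 points, and an odds ratio of 1.25 to 2.0 per point. A two-standard-error difference in mean baseline is 2 × 1.4 × √(2/44) = 0.60 points. On the log-odds scale it shifts the event by 0.60 × ln(OR): 0.13, 0.24 and 0.41 for OR 1.25, 1.5 and 2.0. Dividing by 4, the steepest slope of the logistic curve, gives upper limits of about 3, 6 and 10 percentage points. Averaged over the spread of baselines, the shift is about 5 to 8 points for OR 1.5 to 2.0, against a planned gap of 30 (65% v 35%).

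**4. Power from using baseline.** Simulated trials of 44 v 44 with marginal rates of 65% v 35%; unadjusted chi-square against a model with arm and baseline:

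| Odds ratio per point | Unadjusted | Adjusted |
|---|---|---|
| 1.25 | about 0.79 | 0.82 |
| 1.5 | about 0.79 | 0.84 |
| 2.0 | about 0.79 | 0.86 |

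A check with 4,000 trials per setting, baseline uniform on 95-99% (SD √2 = 1.41) and a logistic likelihood-ratio test gave 0.80 unadjusted and 0.82, 0.85 and 0.89 adjusted. With no relation to baseline at all (OR 1.0), the same test gave 0.82. The gain at OR 1.25 is therefore mostly the choice of test statistic. The gains at 1.5 and 2.0 are real.

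**5. Flicker that is equal in both arms.** Exact enumeration of the uncorrected Pearson test at 44 v 44, with the same event rate in both arms, rejects with probability at most 0.060 at any rate. The harm is dilution. If a fraction f of patients without a true event is scored as events, each rate becomes q = p + (1 − p)f. Starting from 43.75% v 16.25%:

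| f | Rates | Exact power |
|---|---|---|
| 0 | 43.8% v 16.3% | 0.83 |
| 10% | 49.4% v 24.6% | 0.70 |
| 20% | 55.0% v 33.0% | 0.54 |
| 30% | 60.6% v 41.4% | 0.42 |

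**6. Arms at different steady levels.** With SD 1 and 5 readings, controls at 95% and BiPAP at 97% give 84% v 3%, and rejection is near 1. At 97% v 99%, rejection is 0.045. The outcome turns entirely on levels that the documents do not give.

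**The case against.** **The strongest reading does not stand.** A reader might infer that any single stray reading counts as the primary event, and that the test can therefore be significant with no true fall in either arm. The documents do not support this. The single-reading rule is inferred from silence, and the power paragraph names no tier. If the primary event were the tier below 90%, the closeness of entry to the cut would matter far less. Equal flicker does not inflate type I error (step 5). An excess of positive results needs the arms to sit at different steady levels near 94-96%. A 6 L/min cannula against 100% FiO2 makes different levels conceivable, but their position is an assumption. Such a difference would also be a real one in saturation, which the stated hypothesis of improved oxygen saturation partly covers.

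**A fixed cut is a legitimate choice.** It is simple and applies one rule to everyone. That stands, and nothing here requires replacing it with a change from baseline.

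**Baseline may predict less than supposed.** Both arms receive oxygen, which may lift patients away from the cut and weaken the link with entry saturation. Item 1 may also capture a starting value. Both points are fair. The first is why a range of odds ratios is shown. The second still leaves the value unidentified as baseline and unused.

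**A confirming reading is only a partial remedy.** This also stands. A persistent sensor bias would survive an immediate repeat, and a brief true dip may not. That is why confirmation is proposed as a sensitivity analysis and not as a new definition.

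**Conclusion.** The point holds as a matter of efficiency and clarity. Three facts are fixed by the text: the 94% cut is one point below the lowest eligible baseline, baseline saturation is needed for eligibility, and it is neither listed in item 8 nor used in the test. That the 94% tier is primary is the natural reading, because the power paragraph uses the unqualified word that item 1 gives to that tier, but it is not stated.

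The size rests on assumptions about baseline spread, its relation to the event, reading error and number of readings. Within those, adjustment takes power from about 0.79 to 0.82-0.86, with little real gain at the bottom of the range. A two-standard-error imbalance moves event rates by about 5 to 8 points at odds ratios of 1.5 to 2.0. Misclassification shared by both arms costs power and leaves type I error near nominal. This should be changed because the remedy is almost free; it does not invalidate the design.

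**What to change.** 1. **Main change.** Add the eligibility baseline saturation to item 8. In *Data Analysis and Data Monitoring*, analyse the primary event by arm with that value as a covariate, either by logistic regression or by Mantel-Haenszel strata (95-96% v 97% or more). Report it with the planned chi-square, and state before the data are seen which of the two carries the conclusion.
2. **Secondary change.** State that the primary event is the tier of 94% or less, if that is the intent. Log an immediate repeat at each reading of 94% or less, and report the event with and without confirmation as a sensitivity analysis. The monitoring schedule already allows departures when there is an event. Rescue rules are untouched.

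**Cost.** One field on the recording sheet, one extra model and two sentences of text, with no extra patients, staff or devices. The small downside is that a brief true dip may go unconfirmed; it still counts in the unconfirmed version.

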#### **BiPAP settings:**

-IPAP 12 cm H2O/EPAP 6 cm H2O with maximum IPAP 18 cm H2O /8 cm H2O on 100% FiO2 and for a tidal volume of 300-800 mL (target is 450-500)

-If TV are more or less than the 300 to 800 mL range the pressure will be adjusted by 1-2 cm H2O accordingly

CO2 upper endoscopy

Propofol used: divided doses of 50 mg each until loss of eyelash reflex; continual doses as needed until loss of gag reflex

Recording to be done by independent third person

#### **Control group: nasal cannula + BiPAP mask, not connected to machine**

- Nasal cannula set at 6L/min flow rate
- if desaturation below 90 % move to primary rescue maneuver started (nasal cannula removed and BIPAP mask connected to machine)
- If BiPAP rescue maneuvers attempted (adjustments in pressure) and O2 sat is not above 90 % within 3 min of starting BiPAP, secondary rescue maneuver started and scope removed

- Secondary rescue maneuvers performed at the discretion of the anesthesiologist (chin lift, oral airway, bag mask, nasal trumpet, LMA, intubation)
- If sat > 90 % with secondary rescue maneuvers, resumption of scope exam to the discretion of anesthesia
- If sat does not increase > 90 % with secondary rescue maneuvers, scope exam to be cancelled and patient care per anesthesiologist

**Experimental group: BiPAP mask, will connect to machine once sedated**

- If desaturation below 90 % on BiPAP despite increased BiPAP pressures secondary rescue maneuver started and scope removed
- Secondary rescue maneuvers at the discretion of the anesthesiologist (chin lift, oral airway, bag mask, nasal trumpet, LMA, intubation)
- If sat > 90 % with secondary rescue maneuvers, resumption of scope exam at the discretion of anesthesia
- If sat does not increase > 90 % with secondary rescue maneuvers, scope exam to be cancelled and patient care per anesthesiologist

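### As the visible text reads, oxygen during propofol induction may differ between arms; the same cannula in both until BiPAP is connected would be a cheap safeguard

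*Combined protocol and SAP*

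**What the plan says.** All of this is in section iv, Methods and Procedures, of the combined protocol and SAP, unless another place is named.

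- **Control arm.** The heading is "Control group: nasal cannula + BiPAP mask, not connected to machine", and the first bullet is "Nasal cannula set at 6L/min flow rate". No start time for the flow is given. Below 90% the primary rescue is "nasal cannula removed and BIPAP mask connected to machine".
- **Experimental arm.** The heading is "Experimental group: BiPAP mask, will connect to machine once sedated". The bullets beneath it cover rescue only. The first opens "If desaturation below 90 % on BiPAP despite increased BiPAP pressures", so it presupposes that BiPAP is already running.
- **BiPAP settings.** FiO2 of 100% is listed as a machine setting. Propofol is given in "divided doses of 50 mg each until loss of eyelash reflex", with more doses as needed until the gag reflex is lost.
- **End points.** "Desaturation defined as O2 sat" at or below 94% is the first entry under item 1; below 90% is the level that requires intervention. Under item 5 the procedure clock starts with sedation.
- **Data Analysis and Data Monitoring.** The primary outcome is whether a desaturation event occurs, compared between arms of 44.
- **Attachment A.** A decision tree for each arm is titled, but the figures are not shown.

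**The concern.** The stated purpose is to learn whether BiPAP used alongside sedation lowers the incidence of hypoxic episodes. That comparison is clean only if the arms differ by BiPAP and by nothing avoidable. On the page, they also differ in the interval between the first propofol dose and connection of the machine: one arm has a cannula at 6 L/min, and the other has a mask attached to nothing.

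A desaturation in that interval, in a patient assigned to BiPAP, would be charged to BiPAP although BiPAP had not begun. The same interval has no written rescue rule in the experimental arm, because the only trigger there applies to patients already on BiPAP. These are patients with a BMI of 40 to 60 receiving propofol, so the point concerns their care as well as the estimate.

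**Working it through.** **The plan's own figure.** The Data Analysis section gives w = 0.30, two-tailed alpha 0.05 and power 0.80. For a chi-square test with 1 degree of freedom:

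N = (1.960 + 0.842)² / 0.30² = 7.85 / 0.09 = 87.2, rounded up to 88, or 44 per arm.

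The figure reproduces. The present point does not touch it, and the fix leaves N at 88.

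**The two arms before BiPAP is connected, side by side.**

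| | Control | Experimental |
|---|---|---|
| Interface | Cannula plus unconnected mask | Mask, not yet connected |
| Oxygen listed | 6 L/min | None listed; 100% FiO2 is a machine setting |
| Start of that oxygen | Not stated | At connection |
| Written rule below 90% | Remove cannula, connect BiPAP | None before connection |

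**Conditions for a bias.** All four must hold:

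1. Experimental patients receive no oxygen before connection. The text lists none, but does not say that it is withheld.
2. The control cannula flows during induction. This is plausible, but not stated.
3. The interval is long enough for saturation to fall. Divided doses take some time; no length is given, and the point at which a patient counts as sedated is not defined.
4. Events before connection count toward the primary outcome. No text excludes them. The start-of-sedation clock suggests that they may count, but it sits under procedure times, not under the saturation end point.

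**Direction.** If all four hold, let p be the experimental-arm risk with equal oxygen, and q the chance that an otherwise event-free experimental patient has an event because oxygen was missing at induction. The observed risk becomes p + (1 − p)q, which exceeds p whenever q > 0. The error therefore runs against BiPAP.

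**Size.** Neither p nor q is in the documents. The planned w does not supply p, because w = (pC − pT) / (2√(p̄(1 − p̄))) = 0.30 fits many pairs of risks. For example, 30% v 6.8% gives 0.232 / (2 × √(0.184 × 0.816)) = 0.30, and 50% v 21.3% gives 0.287 / (2 × √(0.3565 × 0.6435)) = 0.30. Nothing at all bears on q. A p-value or power loss computed from assumed induction events would show only that a few events matter with 44 per arm, which is true of events from any cause. None is offered.

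**The case against.** The strongest reply is that this argues from silence. The experimental heading says when the machine is connected, not that oxygen is withheld until then. The arm descriptions are short and deal mostly with rescue; routine anesthetic care at induction is not described for either arm. The page most likely to settle the matter, the decision trees, cannot be seen. This stands, and it is why the point is conditional. It does not remove the value of saying in the text what is given.

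Second, this is labelled an effectiveness trial, so delayed connection can be seen as part of the strategy under test. It is right that all events may be counted by assigned arm, and nothing here argues against that. The label does not, however, give a reason for unequal oxygen that has nothing to do with BiPAP.

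Third, an error against BiPAP cannot create a false claim of benefit. That is true, but it can hide a real benefit.

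Fourth, entry requires a baseline saturation above 94%. That helps only a little: in whole-number readings a patient may enter at 95% and meet the definition after a fall of one point.

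Fifth, the Submission Notes report that no patient needed a secondary rescue maneuver. That is reassuring about severe events. It says nothing about falls to 94% or below that resolved without one.

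A reader might go further and infer that experimental patients were induced without oxygen, or that the trial is biased against BiPAP. The documents support neither. Both need the four conditions under the working, and none of these is stated.

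**Conclusion.** The point holds as a worthwhile, inexpensive improvement, on condition that the Attachment A trees do not already cover the interval. On the visible text, listed oxygen differs between the arms during propofol induction, and the experimental arm has no written rule for a fall below 90% before connection. If that text is followed literally, with the control cannula on from the start of sedation and events before connection counted, some desaturations could be charged to BiPAP before it is applied. The direction is against BiPAP; the size cannot be computed from the documents.

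This goes beyond a request for detail, because the change alters what patients receive and protects both the primary comparison and their safety. It falls short of a demonstrated bias.

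**What to change.** 1. In the Experimental group section, give the same 6 L/min cannula as in control from the start of sedation, and remove it when BiPAP is connected. In the Control group section, state that the cannula also runs from the start of sedation. If the Attachment A tree already provides this, repeat it in the text.
2. In the Experimental group section, add that BiPAP is connected at once if saturation falls below 90% before the planned connection.

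**Cost.** One cannula per experimental patient during induction and a few lines of text. Control patients already wear cannula and mask together, and the control rescue already includes the step of removing the cannula and connecting the machine, so nothing new is asked of staff.

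**Downside.** The regimen tested becomes cannula followed by BiPAP. Induction events common to both arms remain and still dilute the contrast. The later difference between 100% FiO2 on BiPAP and 6 L/min by cannula is unchanged.

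**Separate and optional.** The plan could state the window in which primary events count, and could record the connection time so that experimental-arm events before and after it can be described. The plan already has "Recording to be done by independent third person", so the extra time is easy to note. The case for equal oxygen does not depend on either addition.
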